15.3.3. Recording and Reporting of Adverse Events (AEs)

All AEs, as defined above, encountered during the clinical study as well as any **SAEs** (see Section 15.3.2) will be reported in the appropriate section of the CRF. Information will include the following:

- Duration of the AE (onset date and time and resolution date);
- Relationship to ProvayBlueTM (refer to Section 15.3.3.5);
- Time relationship to ProvayBlueTM dosing time;
- Assessment of whether AE is an infusion site reaction;
- Severity (refer to Section 15.3.3.6);
- Outcome of the AE;
- Concomitant treatment dispensed (or other action taken);
- Action taken with respect to the ProvayBlueTM.

If an AE increases in severity it will be recorded as a new record with the same AE identifier.

AE data should be obtained through observation of the patient, from any information volunteered by the patient (and the patient's parent[s]/legal guardian[s]) and through patient (and the patient's parent[s]/legal guardian[s]) questioning. The patient may be asked "Do you have any health problems?" or "Have you had any health problems since your last site visit?"

Refer to Section 15.3.3.9 for guidance relating to reporting of suspected, unexpected serious adverse reactions (SUSARs) to regulatory agencies.

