1. INTRODUCTION AND SCOPE

ProvayBlue™ (methylene blue) was approved under the accelerated approval regulation, 21 CFR 314.510. Provepharm was required to conduct “further adequate and well-controlled studies” to verify and describe the clinical safety and benefit of the agent in therapeutic use for the treatment of acquired methemoglobinemia. To fulfill this requirement, Provepharm has initiated 2 studies and enrollment to both studies are closed at this time.

The first study, protocol PVP-2016003, titled “Open Label Clinical Study to Evaluate the Safety and Efficacy of ProvayBlue™ (Methylene Blue) for the Treatment of Acquired Methemoglobinemia,” was initiated 19 October 2017; the study had enrolled a total of 7 patients when the enrollment was closed on 31 August 2020. This study is referred to hereafter as the Interventional Study. Because of the slow pace of enrollment in this study, doubtless due to the paucity of patients with this ultra-rare disease available for assessment, a stand-alone database, as commonly utilized with clinical trials, has not been setup to capture the data; rather, all clinical data were captured on a paper case report form (CRF).

The second study, protocol HQF-METHB-2018001, titled “Use of Methylene Blue in Acquired Methemoglobinemia: Prospective Observational Registry (metHb),” started May 2018, and enrolled 24 patients before closure on 31 August 2020. This study is referred to hereafter as the Observational Study. The Observational Study was expected to last 2 years after the commencement of enrollment in up to approximately 50 hospital systems. This Observational Study was designed to support low-burden screening and data collection, and to enroll real-world cases of acquired methemoglobinemia treated with ProvayBlue™ without restriction; thus, study sites were more amenable to participate in this program than in the Interventional Study. When enrollment was closed, approximately 90 individual hospitals were approved to enroll patients into the Observational Study; however, only 24 patients were enrolled, again owing to the rarity of the clinical presentation of interest. An electronic database has been set up to house data from both studies.

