2.2. Data Collection

2.2.1. HQF-METHB-2018001

Protocol HQF-METHB-2018001 is designed to be a low-burden minimal-risk **Observational Study**; data collection largely is by passive chart review, with follow-up by telephone or postal mail and/or using medical records where applicable. At some participating study sites, follow-up of acquired methemoglobinemia patients is standard care or part of quality improvement efforts, and some study sites are operating under a full waiver of consent / assent, based on local IRB approvals.

To minimize risk and qualify for the most streamlined study procedures, the **Observational Study** is electronic source (paper forms are not required) and the study data are de-identified to the HIPAA Safe-Harbor standard. Notably, the Safe-Harbor method involves collection of relative “study days” (eg, “Study Day 1, 12:45”) rather than absolute “calendar days” (eg, December 31, 2019, 12:45). Significantly, the “study day” safe-harbor format does not restrict any of the proposed analyses. In our proposed analyses, a pseudo enrollment date was created for each patient when the patient’s case was registered in the database.

To support intuitive and consistent presentation of the data, Study Day 1 Hour 0 is defined as the day and time of the completion of the first methylene blue infusion, and the timing of all study

measurements is presented as the relative time elapsed from this reference point. Thus, a negative relative time indicates that an event/assessment occurred prior to the first infusion completion time, whereas a positive relative time indicates that an event/assessment occurred after the first infusion conclusion time.

To gain understanding about all real-world cases of acquired methemoglobinemia treated with ProvayBlue™, and to encourage more sites to participate by making the enrollment criteria less restrictive, enrollment of a “Secondary Treated Group” was included in the Observational Study. That is, this study groups enrolled patients into two subgroups: Primary cases or Secondary cases.

All primary cases must fulfill the following requirements:

1. Baseline metHb $\geq 30\%$, OR
2. Documented signs or symptoms of methemoglobinemia with subsequent assay of methemoglobin levels above the institutional upper limit of normal (ULN). For these patients, response to the question ‘Were there any signs or symptoms judged to be clinically associated with the acquired methemoglobinemia?’ must be a ‘Yes’

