2.2.1. PVP-2016003

Protocol PVP-2016003 is an open-label, uncontrolled Phase 4 Interventional Study of patients who present in hospital/urgent care setting with acquired methemoglobinemia. The population may include pediatric and adult patients (males and females of all ages are included). Eligible patients will receive a single dose of study drug (typically 1 mg/kg of ProvayBlue™) treatment to treat acquired methemoglobinemia resulting in a direct health benefit. Patients will be followed post treatment; safety, efficacy, and PK data will be collected following a predefined data collection schedule (Table 2).

To create a harmonized electronic database, data collected from this study will be entered into the electronic data collection system used for the Observational Study, and the absolute dates of service recorded in this study will be converted to safe-harbor compliant “study days” before data are entered into the database for analyses. In instances where a specific procedure/data collection time was not initially recorded on the paper CRF, a data query will be generated to obtain the specific time from the site. All patients from this protocol are considered as Primary cases.

The original CRFs for Protocol PVP-2016003 requested posttreatment AE tracking, but the Study Procedure Chart indicates that AEs are tracked pretreatment. To be consistent with the Observational Study, any AEs collected prior to study drug treatment will be identified as NOT treatment-emergent events. Non-treatment-emergent AEs will be included in the data listing but will be excluded from data summary (see Section 6.2 for additional details).

Table 2: Study PVP-2016003 Procedures

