3.1. Database Structure

It is the intention of Provepharm to enter selected, pertinent CRF data elements from the Interventional Study into the database serving the Observational Study for the purpose of preparing the data summary for PMR-3065-1.

It is therefore expected that certain procedures will have to take place before the CRF data elements from the Interventional Study can be entered into the electronic database. Those procedures include but are not limited to converting the absolute calendar dates from the Investigational Study CRFs to the relative study days used in the database. The integrated datasets will mimic the SDTM structure and naming convention whenever possible.

In study PVP-2016003, PK blood draws were planned and plasma concentration were to be determined. However, PK data are not collected due to poor PK blood sample handling. Therefore, the corresponding dataset (PC) will not be created.

In a situation where a data field that is planned in one protocol but not in the other protocol, the missing data will be marked as 'Not Done' in the database. For instance, the Observational - Study (HQB-METHB-2018001) collects "Patient setting before first presentation", "Diagnosed by", "Diagnosis setting". These 3 questions are not included in the Interventional Study. Hence, data value will be set to 'Not Done' in 'Patient setting before first presentation' dataset XD for patients from the Interventional Study (PVP-2016003).

Table 3: Expected SDTM Domains for the Pooled Database

Name of Data Collection Elements/Form	SDTM Domain
Demographics (age, sex, race, ethnicity)	DM
Weight and height at enrollment	VS
Patient setting before first presentation	XD
Past medical history	MH
Acquired methemoglobinemia diagnosis, including diagnosis ICD-10 Code	XD
Methemoglobinemia assessment and treatment before receiving study drug	XD
Methemoglobinemia signs and symptoms	CE
Co-oximetry before and after ProvayBlue™ treatment	LB
Arterial blood gas	LB
ProvayBlue™ administration	EX
Other treatment for methemoglobinemia	CM
Vital signs	VS
ECG	EG
Hematology, biochemistry, and other labs	LB
Medications and procedures	CM, PR
Hospital course	HO
Adverse events	AE
Follow-up overview and questionnaires	QS

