6.2. Adverse Events

Adverse events reported after the first dose of ProvayBlue™ infusion start time and within 10 days after the last dose of ProvayBlue™ infusion will be considered treatment-emergent adverse events (TEAEs). Any AEs that do not have onset time will be included as TEAEs if reported. Patients who did not have any AEs will be verified via source documentation.

The Medical Dictionary for Regulatory Activities (Version 23) will be used to classify all AEs with respect to system organ class and preferred term. All adverse events will be listed.

The following summary tables will be produced for the TEAEs. All data summaries will provide number (%) patients as well as total number of events in each category by patient group. Each summary will be produced in 2 sets: one includes the Primary cases and one includes all patients in the safety analysis set.

1. a topline summary of TEAEs (**Table 14.3.2.1.1**, **Table 14.3.2.1.2**)
2. a summary table by preferred term in descending order of total incidence (**Table 14.3.2.2.1**, **Table 14.3.2.2.2**)
3. a summary table by system organ class and preferred term (**Table 14.3.2.3.1**, **Table 14.3.2.3.2**)
4. a detailed summary table by system organ class, preferred term and severity (**Table 14.3.2.4.1**, **Table 14.3.2.4.2**)
5. a detailed summary table by system organ class, preferred term and relationship (**Table 14.3.2.5.1**, **Table 14.3.2.5.2**)
6. a table of serious TEAEs by system organ class and preferred term (**Table 14.3.2.6.1**, **Table 14.3.2.6.2**)

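### The adverse-event tables pool trial and registry patients whose events were sought in different ways, and no table separates them, so the pooled percentages may be under-ascertained by an unknown amount

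*SAP*

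**What the plan says.** **Pooling.** SAP Section 3.2 puts all treated patients from both studies into one safety set. For the TEAE summaries, SAP Section 6.2 says: "Each summary will be produced in 2 sets: one includes the Primary cases and one includes all patients in the safety analysis set". SAP Section 3.7.3 explains that safety is tabulated twice because Primary and Secondary cases were monitored differently. The other breakdown, in SAP Sections 3.7.2 and 4, is by Dapsone or non-Dapsone cause. Of the trial, SAP Section 2.2.1 (PVP-2016003) says: "All patients from this protocol are considered as Primary cases".

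**How events are found in the trial.** Protocol Section 15.3.3: "AE data should be obtained through observation of the patient, from any information volunteered by the patient", and also by questioning, for example "Have you had any health problems since your last site visit". Protocol Section 12.4 schedules a visit at days 5 to 10 with hematology, biochemistry, physical examination and vital signs, and a call at days 10 to 15. Adverse events are reviewed at follow-up.

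**How they are found in the registry.** SAP Section 2.2.1 (HQF-METHB-2018001): "data collection largely is by passive chart review, with follow-up by telephone or postal mail and/or using medical records where applicable". SAP Section 2.1 adds that institutional care, not the study protocol, sets the timing of registry procedures. Table 3 in SAP Section 3.1 lists a form called "Follow-up overview and questionnaires".

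**By-study presentation.** SAP Section 4.1 plans disposition overall and by protocol (Table 14.1.1). No adverse-event table in SAP Section 7.1 is planned that way.

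**The concern.** The plan accepts that safety data of unequal quality should not be shown only in one pool; that is why it tabulates safety twice. But the split it chose follows monitoring status. Ascertainment differs by study, and both safety tables mix the studies.

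In a TEAE table, a patient with no recorded event adds one to the denominator and nothing to the numerator. A trial patient who was asked, examined and had blood drawn contributes the same zero as a registry patient whose chart happens to be silent. SAP Section 4.1 allows for a 10-day status of unknown or lost to follow-up. SAP Section 3.5 imputes nothing for safety, so such patients stay in the denominator.

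Delayed anemia shows why this could matter. Protocol Section 11.4.2 notes that it may begin one or more days after treatment. The trial's blood tests at days 5 to 10 fall inside the 10-day TEAE window. The SAP describes no equivalent scheduled test for registry patients.

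Safety and tolerability is an objective of both studies (SAP Table 1), and the pooled report is meant to satisfy a post-marketing requirement (SAP Section 1). A reader of the planned tables could not tell whether a low percentage reflects few events or incomplete capture.

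**Working it through.** The documents give no adverse-event rate or capture rate, so there is no stated figure to reproduce. The check has three parts.

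**1. Does any planned split isolate the trial?**
- All-patients tables: trial, registry Primary and registry Secondary together.
- Primary tables: trial and registry Primary together.
- Dapsone and non-Dapsone groups: defined by cause, not by study.

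None does.

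**2. How large could the dilution be?**

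Inputs from SAP Section 1:
- Trial: "the study had enrolled a total of 7 patients when the enrollment was closed on 31 August 2020".
- Registry: "enrolled 24 patients before closure on 31 August 2020".
- Total 7 + 24 = 31; registry share 24/31 = 77%.

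Assumptions, none given in the documents: all enrolled patients were treated; true risk is the same in both studies; the trial captures every event; the registry captures a fraction c of what the trial's methods would have found.

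With m registry patients in a table:

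reported rate / true rate = (7 + m·c) / (7 + m)

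The all-patients table has m = 24. The number of registry Primary cases is not stated, so two values are shown for the Primary table: m = 10 (the planned minimum in SAP Table 1) and m = 17 (arbitrary).

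| c | All patients, m = 24 | Primary, m = 10 | Primary, m = 17 |
|---|---|---|---|
| 1.00 | 31/31 = 1.00 | 17/17 = 1.00 | 24/24 = 1.00 |
| 0.75 | 25/31 = 0.81 | 14.5/17 = 0.85 | 19.75/24 = 0.82 |
| 0.50 | 19/31 = 0.61 | 12/17 = 0.71 | 15.5/24 = 0.65 |
| 0.25 | 13/31 = 0.42 | 9.5/17 = 0.56 | 11.25/24 = 0.47 |

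For an assumed true risk of 20%, the all-patients table would read 16.1%, 12.3% or 8.4% at c = 0.75, 0.50 or 0.25. With m = 10 the Primary table would read 17.1%, 14.1% or 11.2%. Restricting to Primary cases reduces the possible dilution but does not remove it.

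**3. How precise would separate columns be?**

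With zero events in n patients, the exact two-sided 95% upper limit is 1 − 0.025^(1/n):
- n = 7: 41.0%
- n = 24: 14.2%
- n = 31: 11.2%

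An event with a true risk of 10% would be absent from a sample of seven with probability 0.9^7 = 0.48.

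**The case against.** The best defense is that the plan already guards against silent charts. SAP Section 6.2 has patients without adverse events checked against source documents and counts events with no onset time as treatment-emergent. SAP Section 2.2.1 has registry Primary cases fully monitored. The registry is not purely passive: follow-up may be by telephone or post, and the database holds a follow-up questionnaire form. Nor is the trial a clean standard, since its patients may be treated before consent with data collected retrospectively (Protocol Section 12.2). One 10-day window serves both studies. Every event is listed, results are given largely as patient narratives, and the report is descriptive. The SAP says the agency accepted the combined database.

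Much of this stands, and it rules out three stronger readings.

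- A reader might infer that the pooled rates are biased low. The documents do not show that. They give no capture rate, the registry protocol is not among them, and at c = 1 there is no bias.
- A reader might infer that an empty adverse-event field is simply accepted as no event. The source check contradicts that.
- A reader might infer that incidence should be taken from the trial column. Seven patients cannot carry it: 0/7 is compatible with a risk up to 41.0%.

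What the defense does not answer is that a source check can only find what the source contains. Listings might allow a recount by study, but the SAP does not say that the adverse-event listing shows the protocol, and no table does so.

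**Conclusion.** The point holds as a gap in presentation that leaves a plausible bias invisible. The TEAE tables combine two kinds of ascertainment, 77% of enrolled patients come from the registry, and neither planned split follows the difference. The pooled percentages may therefore be under-ascertained. The size is unknown. Under equal true risk, full trial capture and treatment of all 31 enrolled, the all-patients rate would be 0.61 of the true rate at half capture and unchanged at full capture. Dilution in the Primary table would be smaller, but cannot be fixed without the number of registry Primary cases. By-study columns would not measure capture directly, since true risk may also differ between the studies, but they would show a reader what the pooled figure is made of.

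**What to change.** - Add columns by source to Tables 14.3.2.1 to 14.3.2.6: PVP-2016003, registry Primary, registry Secondary, and pooled. Table 14.1.1 already separates the protocols for disposition.
- Footnote each table with how adverse events were ascertained in each column and how many patients in it completed 10-day follow-up.
- Describe pooled percentages in the text as possibly under-ascertained.
- Do not rest the statement of incidence on the seven-patient column alone.

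No new data collection is foreseen. The cost is SAP wording, somewhat more table work, and small columns whose percentages will be imprecise and should be read as counts.

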6.3. Other Safety Parameters

6.3.1. Changes in Other Blood Gas Tests

In addition to metHb, results from 11 other tests obtained via blood gas analysis with or without co-oximetry are collected (Table 5). Individual profiles of the co-oximetry results will be prepared (Figure 14.3.4), showing the observed value (Y) and relative time (X) to the first infusion. Data with assessment time will be included in the graphic display; all data (with and without assessment time) will be included in the data listing (Listing 16.2.12).

Table 5: Blood Gas Parameters of Interest

Parameter (Units)	Data Panel	
	Arterial Blood Gas	Co-Oximetry
1 Total Hemoglobin (g/dL)	Yes	Yes
2 SO ₂ /SaO ₂ (%)	No	Yes
3 C2CT (%)	No	Yes
4 OxyHb (%)	Yes	Yes
5 deoxyHb (%)	No	Yes
6 COHb (%)	No	Yes
7 pH	Yes	Yes
8 PaO ₂	Yes	No
9 PaCO ₂	Yes	No
10 HCO ₃	Yes	No
11 SaO ₂	Yes	No

Abbreviations: SO₂ = oxygen saturation; SaO₂ = arterial oxygen saturation; O₂CT = oxygen content; OxyHb = oxygenated hemoglobin; deoxyHb = deoxyhemoglobin; COHb = carboxyhemoglobin; pH = hydrogen ions (H⁺) in blood; PaO₂ = partial pressure of oxygen; PaCO₂ = partial pressure of carbon dioxide; HCO₃ = Bicarbonate.

6.3.2. Changes in Laboratory Tests

Selected safety laboratory tests of interest will be collected (see Table 6). All laboratory results were from local laboratory. Although other laboratory tests outside this list could be collected, for the purpose of the data summary, the results of laboratory tests collected in 'Other Labs' will only be available in the listing (Listing 16.2.11.3).

Table 6: Safety Laboratory Tests of Interest

Hematology	Biochemistry
Hemoglobin	Glucose
Platelet Count	Sodium
Red Blood Cell Count	Potassium
White Blood Cell Count	Chloride
	Urea
	Calcium
	Inorganic Phosphorus
	Creatinine

Laboratory results will be graphically displayed by patient, showing the observed value (Y) and relative time (X) after the first dose of ProvayBlue™ Infusion (Figure 14.2.5 for hematology, Figure 14.3.6 for Chemistry).

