11.4.2. Hemolytic Anemia

Hemolysis can occur during treatment of methemoglobinemia with ProvayBlueTM. Laboratory testing may show Heinz bodies, elevated indirect bilirubin and low haptoglobin, but the Coombs test is negative. The onset of anemia may be delayed 1 or more days after treatment with ProvayBlueTM. In the event that a patient has hemolytic anemia, discontinue ProvayBlueTM and initiate appropriate treatment (e.g. red blood cell transfusion). Refer also to APPENDIX 1: US Package Insert of ProvayBlueTM for further information.

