15.2.3. Biochemistry

Biochemistry samples will be analyzed by the hospital laboratory.

The following biochemistry parameters will be collected:

- Sodium
- Potassium
- Chloride
- Urea
- Creatinine
- Calcium
- Inorganic phosphorous
- Total Protein
- Albumin
- Gamma glutamyl transferase
- Bilirubin (Total)
- Alkaline phosphatase
- Aspartate transaminase
- Alanine aminotransferase
- Glucose

Additional (optional) biochemistry parameters (for example blood gas) will be collected based on available data from patient standard of care.

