Eye disorders: eye pruritus, ocular hyperemia, vision blurred

Gastrointestinal disorders: abdominal pain lower, dry mouth, flatulence, glossodynia, tongue eruption

General disorders and administration site conditions: death, influsion site extravasation, influsion site induration, influsion site pruritus, influsion site swelling, infusion site urticaria, peripheral swelling, thirst

Investigations: elevated liver enzymes

Musculoskeletal and connective tissue disorders: myalgia

Renal and urinary disorders: dysuria

Respiratory, thoracic and mediastinal disorders: nasal congestion, oropharyngeal pain, rhinorrhea, sneezing

Skin and subcutaneous tissue disorders: necrotic ulcer, papule, phototoxicity

Vascular disorders: hypertension

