3.4. Test Hypothesis and P Value Justification

Not applicable since no inferential statistics will be provided for this PMR. Whenever it is appropriate, 2-sided 95% confidence intervals will be provided for estimates.

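### SAP Table 6 omits total bilirubin and the four liver enzymes that the protocol collects, so the laboratory profiles show no liver test and show haemolysis only through haemoglobin and red cell count

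*SAP*

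**What the plan says.** Protocol 15.2.3 introduces a fixed panel: "The following biochemistry parameters will be collected". It has 15 tests, among them total bilirubin, gamma glutamyl transferase (GGT), alkaline phosphatase (ALP), aspartate transaminase (AST) and "Alanine aminotransferase" (ALT). The flow chart in Protocol Appendix 2 schedules biochemistry and haematology at the same times: screening, after dosing, 24 hours, discharge and the Day 5-10 visit.

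SAP 6.3.2 says "Selected safety laboratory tests of interest will be collected" and refers to Table 6, which names 8 biochemistry and 4 haematology tests. Results are plotted per patient over time. Tests outside the table may be collected, but they go only to Listing 16.2.11.3. SAP 3.1 describes the data transfer as an intention to "enter selected, pertinent CRF data elements from the Interventional Study" into the registry's database. Details are left to a Data Integration Plan (SAP 3).

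On the risks, Protocol 11.4.2 says of haemolysis: "Laboratory testing may show Heinz bodies, elevated indirect bilirubin and low haptoglobin". The package insert (Protocol Appendix 1, section 6.1) lists haemolysis and hyperbilirubinaemia among reactions reported with methylene blue class products, and also "elevated liver enzymes".

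**The concern.** SAP 3.3.3 makes laboratory results before and after treatment a safety endpoint to be summarised. SAP 7.1 contains no laboratory summary table, so the profile figures carry that endpoint. A test missing from Table 6 has no planned display other than a listing.

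The omitted tests are the ones closest to the product's known reactions, while glucose, chloride and calcium are kept. Haemolytic anaemia is a warning in the package insert and its onset may be delayed by a day or more. The protocol schedules bilirubin at the same visits as haemoglobin, including Day 5-10, so the two could be read together. In this small descriptive safety report, a reader who sees haemoglobin fall in one patient will want bilirubin on the same time axis, and the planned figures do not supply it.

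**Working it through.** No error rate or sample size is involved. SAP 3.4 says of hypothesis testing: "Not applicable since no inferential statistics will be provided for this PMR". The check is a comparison of lists.

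**Step 1. Biochemistry, Protocol 15.2.3 against SAP Table 6.**

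| Group | Tests | In Table 6 |
|---|---|---|
| Electrolytes, renal, glucose | sodium, potassium, chloride, calcium, inorganic phosphorus, urea, creatinine, glucose | 8 of 8 |
| Liver-related | total bilirubin, GGT, ALP, AST, ALT | 0 of 5 |
| Proteins | total protein, albumin | 0 of 2 |

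Total: 15 − 8 = 7 omitted, including all 5 liver-related tests. SAP 6.3.2 gives no reason.

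**Step 2. Haematology, Protocol 15.2.4 against Table 6.** Haemoglobin, red cells, white cells and platelets are kept; only the differential count is dropped. SAP Table 5 adds total haemoglobin from blood gas and co-oximetry. Of the three protocol tests that bear on haemolysis (haemoglobin, red cell count, total bilirubin), 2 of 3 are profiled.

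**Step 3. Where the omitted tests can appear.** SAP 7.1 has profile figures for haematology and biochemistry and no laboratory table. SAP 7.2 has Listing 16.2.11.3 for other tests. Protocol 16.5 planned descriptive statistics for laboratory data, but SAP section 1 says that the SAP supersedes the protocol's statistical section.

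**Step 4. Whether the values reach the database.** SAP Table 3 expects a laboratory domain covering haematology, biochemistry and other tests. It does not name individual tests. SAP 3.1 transfers only selected elements, and 6.3.2 is permissive about tests outside Table 6. Entry of bilirubin and the enzymes is neither excluded nor assured.

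**Step 5. Reach.** SAP section 1 gives 7 interventional and 24 registry patients: 7 + 24 = 31, and 7/31 = 23%. The protocol panel applies to the 7. The documents do not say whether the registry recorded these tests.

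**The case against.** The strongest reply is that little is lost. Haemoglobin and red cell count are plotted for each patient, and haematology is repeated at about 24 hours or discharge and at Day 5-10, so delayed anaemia would be seen. SAP 4 promises a patient-level listing of everything in the pooled database. With 31 patients reported mainly through narratives, a listing and a figure differ mostly in presentation. Laboratory abnormalities that need intervention or further investigation are adverse events (Protocol 15.3.1). Haemolytic anaemia is a mandatory reason for discontinuation from the study (Protocol 9.5.1).

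Most of this stands, and it rules out several stronger readings that a reader might infer:

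- **That the profiles cannot show haemolysis.** They can show its main consequence, a fall in haemoglobin and red cells. What is missing is one corroborating test.
- **That adding bilirubin would settle the cause of a fall.** The protocol names Heinz bodies, indirect bilirubin and haptoglobin as signs, yet its panel has only total bilirubin. That helps but is not decisive.
- **That the values are lost.** Non-entry is possible under SAP 3.1, but nothing states it. Values that are entered would be listed.
- **That liver effects rank with haemolytic anaemia as a labelled risk.** Raised liver enzymes appear only in a list of other class reactions, not among the warnings.

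The reply does not explain why these five tests were left out. It also does not cover changes too small to be adverse events: a listing would hold them only if they are entered, and it would not set them against haemoglobin over time.

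**Conclusion.** The point holds as a minor gap in safety reporting. Table 6 drops total bilirubin, GGT, ALP, AST and ALT without a stated reason. The profiles therefore show 0 of 5 liver-related tests, and 2 of the 3 protocol tests that bear on haemolysis. No efficacy result is affected, and the adverse event tables still capture clinically important events.

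Two assumptions underlie this. First, Table 6 is taken to define what the profile figures contain, which is the natural reading of SAP 6.3.2. Second, the scheduled values are taken to exist for the 7 interventional patients. Because treatment may precede consent, some early values may depend on what the hospital measured as routine care. The Data Integration Plan is not among the documents and may already settle the question of entry.

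**What to change.** Add total bilirubin, GGT, ALP, AST and ALT to SAP Table 6 and to the biochemistry profile figure for every patient who has values, at least the 7 interventional patients. State in the Data Integration Plan that these five tests are entered in the pooled database. If the sponsor prefers to keep them as listing-only, the SAP should give the reason and still confirm entry.

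The figure numbers should be aligned in the same edit: SAP 6.3.2 cites Figures 14.2.5 and 14.3.6, while SAP 7.1 numbers the haematology and biochemistry profiles 14.3.4 and 14.3.5.

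The cost is entry of existing values from 7 paper case report forms, plus whatever the registry holds, and extra panels in a figure already planned. No new sampling is needed. Registry values may be sparse, in which case the added panels will show mainly the interventional patients.
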